9.1.1. Adverse Events Leading to Withdrawal

A summary of incidence rates (frequencies and percentages) of TEAEs leading to withdrawal of study drug, by treatment group, SOC, and PT will be prepared for both the Double-blind Period and OLE.

A data listing of AEs leading to withdrawal of study drug during each period will also be provided, displaying details of the event(s) captured on the CRF.

9.1.2. Deaths and Serious Adverse Events

Any deaths that occur during the study will be listed.

Serious adverse events will be listed and also tabulated by SOC and PT and presented by treatment group for the Double-blind Period and overall for the OLE.

9.2. Clinical Laboratory Evaluations

Laboratory tests (clinical chemistry, hematology, coagulation, and quantitative urinalysis) will be performed at Screening, Baseline, Day 30, Day 90, Day 120, and Day 180. Results will be summarized descriptively by treatment group and study visit as both observed values and change from baseline values for the Double-blind Period and OLE. See Section 6.1.1 for the definition of baseline. Number and percentage of subjects with abnormal qualitative urinalysis results will be provided by treatment group and study visit.

The number of subjects with clinical laboratory values below, within, or above normal ranges, by study visit will be tabulated (shift tables) for each clinical laboratory parameter by treatment group.

Laboratory values will be displayed in the data listings and those that are outside the normal range will be flagged and presented along with corresponding normal ranges (if available). A separate listing of abnormal laboratory values will be provided. All study visits within a parameter for a subject will be presented if at least 1 study visit within that parameter has an abnormal result.

Serology results and pregnancy test results will be listed separately.

9.3. Vital Signs

Vital signs will be collected at Screening, Baseline, Day 14, Day 30, Day 60, Day 90, Day 120, Day 150, Day 180, and Day 194. Descriptive summaries of actual values and changes from baseline will be calculated for systolic blood pressure (mmHg), diastolic blood pressure (mmHg), and pulse (bpm).

The number of subjects with vital sign values below, within, or above normal ranges, by study visit will be tabulated (shift tables) for each parameter by treatment group.

These summaries will be presented by study visit and treatment group. See Section 6.1.1 for the definition of baseline.

9.4. Electrocardiograms

12-Lead ECGs will be collected at Screening, Baseline, Day 30, Day 90, Day 120, and Day 180. For subjects in the PK substudy, additional ECGs will be performed postdose during serial blood sampling on Day 1 and Day 30. Descriptive summaries will be presented for heart rate (bpm),

PR interval (ms), QRS interval (ms), uncorrected QT interval (ms), QTcF (ms). These summaries will be presented by study visit and treatment group.

The number and percentage of subjects with normal and abnormal ECG results will be summarized by treatment group and study visit.

9.5. Local Tolerability

During all clinic visits, the investigator will assess local tolerability (Scale: 0-3 [none, mild, moderate, severe]) for each treated body area (chest/abdomen, back, arms, legs, and face/neck).

Descriptive summaries of the investigator's assessment of erythema, stinging/burning, and pruritus will be presented by body area, period, treatment group, and study visit.

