2.2. Study Endpoints

2.2.1. Safety Endpoints

The safety endpoints of this study include the following:

- Reported serious adverse events (SAEs), treatment-emergent AEs (TEAEs), and changes in clinical laboratory tests, vital signs, physical examinations, and 12-lead electrocardiograms (ECGs)
- Local tolerability (Scale: 0-3 [none, mild, moderate, severe], determined by the investigator) for each body area (chest/abdomen, back, legs, arms, and face/neck).

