6.1. Statistical Definitions and Algorithms

6.1.1. Baseline

The last nonmissing assessment recorded prior to the first dose of treatment in the Double-blind Period will be used as the baseline observation for all calculations of change from baseline, including those in the OLE.

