14.3.6.3.1	Safety	Summary of Local Tolerability Assessments by Study Visit	Unique
14.3.6.3.2	OLE Safety	Summary of Local Tolerability Assessments by Study Visit	Non-unique
14.3.6.4.1	Safety	Summary of Physical Examination Results by Study Visit	Unique
14.3.6.4.2	OLE Safety	Summary of Physical Examination Results by Study Visit	Non-unique
14.3.6.5.1	Safety	Summary of Concomitant Medications by ATC Class Level 4 and Preferred Term	Non-unique
14.3.6.5.2	OLE Safety	Summary of Concomitant Medications by ATC Class Level 4 and Preferred Term	Non-unique

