Severe	XX (XX.X%)	XX (XX.X%)	XX (XX.X%)	XX (XX.X%)	XX (XX.X%)
Stinging/Burning					
None	XX (XX.X%)	XX (XX.X%)	XX (XX.X%)	XX (XX.X%)	XX (XX.X%)
Mild	XX (XX.X%)	XX (XX.X%)	XX (XX.X%)	XX (XX.X%)	XX (XX.X%)
Moderate	XX (XX.X%)	XX (XX.X%)	XX (XX.X%)	XX (XX.X%)	XX (XX.X%)
Severe	XX (XX.X%)	XX (XX.X%)	XX (XX.X%)	XX (XX.X%)	XX (XX.X%)
Pruritus					
None	XX (XX.X%)	XX (XX.X%)	XX (XX.X%)	XX (XX.X%)	XX (XX.X%)
Mild	XX (XX.X%)	XX (XX.X%)	XX (XX.X%)	XX (XX.X%)	XX (XX.X%)
Moderate	XX (XX.X%)	XX (XX.X%)	XX (XX.X%)	XX (XX.X%)	XX (XX.X%)
Severe	XX (XX.X%)	XX (XX.X%)	XX (XX.X%)	XX (XX.X%)	XX (XX.X%)

Note: Percentages are n/Number of subjects in the Safety population within actual treatment group and overall*100.
[1] Baseline is defined as the last non-missing assessment recorded prior to the first dose of treatment in the Double-blind Period.
SOURCE: Listing 16.2.9.3

Programming note: Continue for Back, Arms, and Legs. Visits will be Baseline [1], Day 14, Day 30, Day 60, and Day 90.

Table 14.3.6.3.2
Summary of Local Tolerability Assessments by Study Visit
OLE Safety Population

Same shell as Table 14.3.6.3.1

Programming note: Continue for Back, Arms, and Legs. Visits will be Baseline [1], Day 104, Day 120, and Day 150. Update Note: to read "Note: Percentages are n/Number of subjects in the OLE Safety population within treatment group*100. All subjects received Trifarotene cream HE1 200 ug/g in the OLE." Add OLE = open label extension to Abbreviations.

Table 14.3.6.4.1
Summary of Physical Examination Results by Study Visit
Safety Population

Study Visit: XXXXX

Body System Result Clinically Significant?	Trifarotene cream HE1 100 ug/g (N=XX)	Trifarotene cream HE1 200 ug/g (N=XX)	Overall Trifarotene cream HE1 (N=XX)	Vehicle (N=XX)	Overall (N=XX)
Body System 1					
Not Done	XX (XX.X%)	XX (XX.X%)	XX (XX.X%)	XX (XX.X%)	XX (XX.X%)
Normal	XX (XX.X%)	XX (XX.X%)	XX (XX.X%)	XX (XX.X%)	XX (XX.X%)
Abnormal	XX (XX.X%)	XX (XX.X%)	XX (XX.X%)	XX (XX.X%)	XX (XX.X%)
Yes	XX (XX.X%)	XX (XX.X%)	XX (XX.X%)	XX (XX.X%)	XX (XX.X%)
No	XX (XX.X%)	XX (XX.X%)	XX (XX.X%)	XX (XX.X%)	XX (XX.X%)
Body System 2					
Not Done	XX (XX.X%)	XX (XX.X%)	XX (XX.X%)	XX (XX.X%)	XX (XX.X%)
Normal	XX (XX.X%)	XX (XX.X%)	XX (XX.X%)	XX (XX.X%)	XX (XX.X%)
Abnormal	XX (XX.X%)	XX (XX.X%)	XX (XX.X%)	XX (XX.X%)	XX (XX.X%)
Yes	XX (XX.X%)	XX (XX.X%)	XX (XX.X%)	XX (XX.X%)	XX (XX.X%)
No	XX (XX.X%)	XX (XX.X%)	XX (XX.X%)	XX (XX.X%)	XX (XX.X%)
...					

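### Local tolerability is tabulated only as by-visit score distributions, so the number of subjects who newly develop or worsen in a sign, and the worst score reached, cannot be read, most notably in the OLE

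*SAP*

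**What the plan says.** Section 2.2.1 names the endpoint: "Local tolerability (Scale: 0-3 [none, mild, moderate, severe], determined by the investigator) for each body area". Table 1 schedules the assessment at Baseline and at each double-blind clinic visit, and section 3.4 has the first dose applied after the baseline measurements. Baseline scores are therefore pre-dose.

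Section 9.5 plans descriptive summaries only: "assessment of erythema, stinging/burning, and pruritus will be presented by body area, period, treatment group, and study visit". The planned table list in section 13.3 has two tolerability tables, for the Safety and OLE Safety populations, both titled "Summary of Local Tolerability Assessments by Study Visit". The shell has rows for none, mild, moderate and severe within each sign and body area, one block per visit. Its double-blind note reads "Continue for Back, Arms, and Legs. Visits will be Baseline [1], Day 14, Day 30, Day 60, and Day 90" and its OLE note reads "Continue for Back, Arms, and Legs. Visits will be Baseline [1], Day 104, Day 120, and Day 150". Neither table has a change from baseline, a shift, a count of subjects who worsened, or a worst post-baseline score. Listing 16.2.9.3 shows the score alone, without the baseline and change columns used in the efficacy, laboratory, vital sign and ECG listings.

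For laboratory values, by contrast, section 9.2 says that counts below, within or above the normal range "will be tabulated (shift tables) for each clinical laboratory parameter by treatment group". Section 9.3 says the same for vital signs. Section 6.1.1 defines the reference: "The last nonmissing assessment recorded prior to the first dose of treatment in the Double-blind Period will be used as the baseline observation", and applies it to change calculations in the OLE as well.

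**The concern.** Erythema, stinging/burning and pruritus can be present before any cream is applied. A table of separate visit distributions does not link a subject's later score to that subject's own baseline. Improvement in some subjects and new reactions in others can offset each other within an arm, and the number of subjects ever affected cannot be recovered from the visit counts.

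Two features of this plan give the gap some weight. First, section 3.4 reduces application on an area scored 2 and stops it on an area scored 3, until the score falls. A subject who is moderate at Day 14 may be mild by Day 60 because less cream was applied. Without a worst post-baseline score, that subject and another who is first moderate at Day 60 are never counted together as affected. Second, the OLE has no vehicle arm, and former vehicle subjects first receive active cream there. The OLE table shows the double-blind Baseline and then Days 104, 120 and 150, but not Day 90, the last score before that switch.

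At stake is the description of a named safety endpoint of a topical product. Section 9 plans no formal safety inference, so these tables carry the conclusion.

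**Working it through.** The plan states no figure on this point, so there is none to reproduce. The check is what the planned tables can and cannot identify. All rates and counts below are assumed, because the SAP gives no baseline frequency of these signs.

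**Inputs.** 65 subjects enrolled (section 1), randomised 1:1:1 (section 3.5). 65/3 = 21.7, so about 22 per arm if the split is even. Four post-baseline double-blind visits (shell for Table 14.3.6.3.1).

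**Step 1: new onset at one visit, one arm.** With n subjects, b having the sign at baseline and v at the visit, the number of new cases lies between max(0, v − b) and min(v, n − b). For n = 22 and b = v, where the table shows no change:

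| b = v | New cases possible | Upper limit, % of arm |
|---|---|---|
| 2 | 0 to 2 | 9.1 |
| 4 | 0 to 4 | 18.2 |
| 6 | 0 to 6 | 27.3 |
| 8 | 0 to 8 | 36.4 |
| 11 | 0 to 11 | 50.0 |

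Two arms with identical entries of 6/22 and 6/22 could therefore have 0 and 6 new reactions.

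**Step 2: the same question with the vehicle arm included.** Let b be the baseline proportion, r the proportion of those who improve, and w the proportion of the rest who newly worsen. The visit proportion is b(1 − r) + (1 − b)w. Assume moderate or severe signs with b = 0.30 and r = 0.50 in both arms, w = 0.20 on active and w = 0 on vehicle:

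- Active: 0.30 × 0.50 + 0.70 × 0.20 = 0.15 + 0.14 = 0.29
- Vehicle: 0.30 × 0.50 = 0.15
- Gap: 0.29 − 0.15 = 0.14, or about 3 of 22 (0.14 × 22 = 3.1)

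The active arm alone moves only from 30% to 29%, but the 14-point gap against vehicle equals the new-reaction rate and would show in the planned double-blind table. In general, with equal baselines, the gap is b(r_vehicle − r_active) + (1 − b)(w_active − w_vehicle). It isolates new reactions only if pre-existing signs improve equally in both arms.

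**Step 3: number ever affected.** With counts v1 to v4 at the four visits, the number affected at least once lies between the largest count and the smaller of n and the sum. If 3 of 22 are moderate or severe at each visit, this is 3 (13.6%) to 3 × 4 = 12 (54.5%). The vehicle column does not narrow this range.

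**Step 4: the OLE.** There is no vehicle column, so the contrast in step 2 is unavailable. Day 90 appears only in the double-blind table, which covers a different population. Section 5 has OLE analyses by actual treatment received, which is 200 µg/g for everyone. On that reading, former vehicle subjects are not shown separately either.

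**The case against.** The strongest reply is that the double-blind table already shows Baseline and Vehicle beside the two active arms. Step 2 bears this out. A reader might infer from the missing shift table that drug reactions would go unseen, or that chance baseline imbalance passes unnoticed into the comparison of arms. The document does not support either inference for the double-blind period. The contrast with vehicle is displayed, imbalance can be seen in the Baseline block, and no safety test is planned that could be distorted.

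Further points have some force:

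- The rules in section 3.4 act on the absolute score, and by-visit counts of moderate and severe show how many subjects stood at those levels at each visit.
- Subject-level scores are listed, the diary listing records cream reactions and untreated areas, and adverse event tables cover events that start or worsen after first dose. This is partial cover. The SAP states no rule linking a tolerability score to an adverse event, and readers would have to rebuild shifts by hand across five areas and three signs.
- The laboratory precedent is not universal. ECG interpretation and physical examination are also shown by visit without shifts, and the vital sign shifts promised in section 9.3 have no table in the list. On this point section 9.5 and its shells agree with each other, so there is no internal contradiction.
- A worst-score shift has its own bias. Taking the worst of four visits against one baseline raises apparent worsening in every arm.

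What survives is the within-subject information: new onset, worsening and the number ever affected in both periods, with the OLE the weaker of the two.

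**Conclusion.** The point holds as a gap in the descriptive display, not as an error in the plan. From the planned tables, net group change and the contrast with vehicle can be read in the double-blind period. The number of subjects newly affected or worsened and the worst score reached cannot. In the OLE even the vehicle contrast is absent, and the last score before the change to open-label cream is not tabulated.

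The size cannot be stated from the document. The ranges above (0 to 6 new cases in 22 behind an unchanged 6/22, and 3 to 12 ever affected behind 3/22 at each of four visits) are arithmetic limits under assumed counts and an even split of 65 subjects. They are not estimates of what happened. This is an inexpensive improvement that is worth making while it can still be prespecified, since section 1 says the SAP is filed before any unblinded analysis.

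**What to change.** Add to section 9.5, the table list and the shells:

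1. **Double-blind period.** By arm, sign and body area, a shift from Baseline to the worst post-baseline score. Include the number and percentage of subjects worsening by at least 1 grade in any body area, and the number newly reaching moderate or severe. Compare each area with its own baseline. A maximum taken over areas would hide a new reaction on one area behind an old one of equal grade on another. State that worsening is to be read against the vehicle arm, because the worst of several visits raises it everywhere.
2. **OLE.** Add Day 90 to the table, and give a shift from Day 90 to the worst OLE score by former double-blind arm. Describe it as a supplementary exception to section 6.1.1, which otherwise fixes the pre-dose double-blind baseline. For subjects already on active cream, Day 90 may itself carry reactions to the cream, which is why the split by former arm is needed.
3. **Definition of worst score.** Say which assessments count. Section 9.5 includes face/neck, but the shell notes stop at back, arms and legs. Table 2 schedules tolerability at Day 180, but the OLE shell stops at Day 150. Those are separate discrepancies, but the new tables should not inherit them. State also whether unscheduled assessments count, given section 6.1.5.

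The cost is one or two extra descriptive tables from scores already collected, with no new assessments.

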9.6. Physical Examination

Physical examinations will be performed at Screening, Baseline, Day 90, Day 180, and Day 194. The number and percentage of subjects with normal and abnormal findings in the complete physical examination will be displayed for each treatment group in each period.

9.7. Concomitant Medication

Prior and concomitant medications, coded using World Health Organization-Drug Dictionary Enhanced (WHO-DDE) (September 2018), will be summarized descriptively by Anatomical Therapeutic Chemical (ATC) classification Level 4 and PT (i.e., ATC classification Level 5), if applicable, using counts and percentages for the Safety Population.

Prior medications and concomitant medications will be presented separately. The assignment of medications as prior and/or concomitant will be done as follows:

- **Prior medications:** Medications that started before the first dose of study drug will be considered prior medications whether or not they were stopped before dose.
- **Concomitant medications:** Any medications continuing or starting after the first dose of study drug through the end of study will be considered to be concomitant.

If a medication starts prior to the first dose and continues after the first dose it will be considered both prior and concomitant. Prior and concomitant medications will also be listed. Prior and concomitant medications will be summarized descriptively by treatment using counts and percentages.

9.8. COVID-19 Visit Impact

A listing of the COVID-19 visit impact log will be presented which will display which (if any) study visits were impacted by the pandemic. The listing will display if the visit was performed and if the visit type was adjusted as well as the reason(s) for adjustment.

10. Changes from Planned Analysis

Age was added as a factor for MMRM analyses because the study is enrolling both adults and

adolescents.

11. Other Planned Analysis

11.1. Pharmacokinetic Analysis

The pharmacokinetic characterization of drug concentrations for each dose to be profiled will use noncompartmental analysis (NCA).

Samples for PK will be drawn from all subjects at Baseline and at each clinic visit for trough values. Subjects who provide written informed consent to participate in the optional PK substudy will provide blood samples for PK analysis predose on Day 1 and at 1, 2, 4, 8, 12, and 24 hours postdose on Day 1 and Day 30.

The PK parameter estimates will be completed using WinNonlin (Pharsight Corporation) software using the actual elapsed times from dose administration to sample collection (i.e., not nominal time).

Standard PK parameters assessed will include measures of the extent of absorption using estimates of the Area under the plasma concentration-time curve from time 0 to the time of the last quantifiable plasma concentration (AUC_{0-t}), Area under the plasma concentration-time curve from time 0 to infinity (if data permits) (AUC_{0-inf}) and rate-of-absorption using the maximum serum concentration (C_{max}), the time of C_{max} (T_{max}), apparent first order terminal elimination half-life ($t_{1/2}$), apparent terminal phase rate constant (λ_z) (if data permits).

For noncompartmental analysis, plasma concentrations will be listed and summarized at each time point using descriptive statistics. Descriptive statistics reported will include the arithmetic mean, SD, CV%, geometric mean, minimum, maximum, and median. Only the range and the median will be reported for T_{max} , as this is a categorical parameter. The PK parameters will also be summarized by treatment using descriptive statistics.

Individual plasma concentration plots and mean data graphs will be produced using both linear and semi-logarithmic scales. Mean data graphs will show plasma concentration profiles by treatment group. Pharmacokinetic plasma parameter estimates and summaries will be completed for the subjects in the PK population.

- Adverse events with missing MedDRA coding will have their system organ class and/or

preferred term presented as “Not Coded” in the tables. The “Not Coded” frequencies will be sorted to the end of the tables. This will only be applicable for any deliveries sent before database lock (e.g., for dry runs on blinded data).

- Programming notes may be inserted into the shells, these notes will not appear in the final output.

Population Summary Conventions

- Population sizes may be presented for each classification factor as totals in the column header as (N=xxx), where appropriate.
- All population summaries for categorical variables will include all categories that were planned and for which the subjects may have had a response. Percentages corresponding to null categories (cells) will be suppressed; however, counts and percentages of missing values may be needed.
- All population summaries for continuous variables will include: N, mean, SD, median, minimum, and maximum. Other summaries (e.g., number missing, 95% CIs) may be used as appropriate. The precision of the maximum and minimum will match the maximum precision in the data. The mean and median will have 1 additional decimal place. The SD will have 2 additional decimal places.
- All percentages are rounded (where, for example, 0.05% is rounded up to 0.1%) and reported to a single decimal point (xx.x%).
- A percentage of 0% will not be displayed (i.e., only the count of 0 will be displayed), and a percentage of 100% will be displayed with 0 decimal places.
- All *P* values will be displayed in four decimals and rounded using standard scientific notation (e.g., 0.XXXX). If a *P* value less than 0.0001 occurs it will be shown in tables as <0.0001.

13.1. Planned Table Descriptions

The following are planned summary tables for protocol number 18-ICH-001. The table numbers and page numbers are place holders only and will be determined when the tables are produced.

Table 9: Demographic Data Summary Tables and Figures

Number	Population	Title	Unique/Non-unique
Table 14.1.1.1	ITT	Summary of Subject Disposition	Unique
Table 14.1.1.2	OLE ITT	Summary of Subject Disposition	Non-unique
Table 14.1.2.1	ITT	Demographics and Baseline Characteristics	Unique
Table 14.1.2.2	OLE ITT	Demographics and Baseline Characteristics	Non-unique
Table 14.1.3	Safety	Summary of Medical Histories by System Organ Class and Preferred Term	Unique
Table 14.1.4	Safety	Summary of Prior Medications by ATC Class Level 4 and Preferred Term	Unique
Table 14.1.5.1	Safety	Summary of Drug Accountability (Drug Returned and Dispensed)	Unique
Table 14.1.5.2	OLE Safety	Summary of Drug Accountability (Drug Returned and Dispensed)	Non-unique
Table 14.1.5.3	Safety	Summary of Treatment Exposure and Compliance	Unique
Table 14.1.5.4	OLE Safety	Summary of Treatment Exposure and Compliance	Non-unique

13.2. Efficacy Data

Table 10: Efficacy Data

Number	Population	Title	Unique/Non-unique
14.2.1.1.1	ITT	Primary Analysis: Logistic Regression Analysis of Successful Resolution of LI	Unique
14.2.1.1.2	OLE ITT	Proportion of Subjects with Successful Resolution of LI in the OLE	Unique
14.2.1.2.1	mITT	Primary Analysis, Sensitivity: Logistic Regression Analysis of Successful Resolution of LI	Non-unique
14.2.1.2.2	OLE mITT	Proportion of Subjects with Successful Resolution of LI in the OLE	Non-unique
14.2.1.3.1	PP	Primary Analysis, Sensitivity: Logistic Regression Analysis of Successful Resolution of LI	Non-unique

Number	Population	Title	Unique/Non-unique
14.2.1.3.2	OLE PP	Proportion of Subjects with Successful Resolution of LI in the OLE	Non-unique
14.2.1.4	ITT	Primary Analysis, Sensitivity: Logistic Regression Analysis of Successful Resolution of LI Using Multiple Imputation	Non-unique
14.2.1.5.1	ITT	Logistic Regression Analysis of 50% Reduction in IGA score from Baseline	Non-unique
14.2.1.5.2	OLE ITT	Proportion of Subjects with a 50% Reduction in IGA score from Baseline	Non-unique
14.2.1.6.1	ITT	MMRM Analysis of Change from Baseline in IGA Score	Unique
14.2.1.6.2	OLE ITT	MMRM Analysis of Change from Baseline in IGA Score	Non-unique
14.2.1.7.1	ITT	Categorical IGA Scores	Unique
14.2.1.7.2	OLE ITT	Categorical IGA Scores	Non-unique
14.2.2.1	ITT	Secondary Analysis: MMRM Analysis of Change from Baseline in VIIS Score	Non-unique
14.2.2.2	OLE ITT	MMRM Analysis of Change from Baseline in VIIS Score	Non-unique
14.2.3.1	ITT	Secondary Analysis: MMRM Analysis of Change from Baseline in Individual Score for Roughness	Non-unique
14.2.3.2	OLE ITT	MMRM Analysis of Change from Baseline in Individual Score for Roughness	Non-unique
14.2.3.3	ITT	Logistic Regression Analysis of 2-grade Change in Individual Score for Roughness from Baseline	Non-unique
14.2.4.1	ITT	Secondary Analysis: MMRM Analysis of Change from Baseline in Palm/Sole Assessment	Non-unique
14.2.4.2	OLE ITT	MMRM Analysis of Change from Baseline in Palm/Sole Assessment	Non-unique
14.2.4.3	ITT	Logistic Regression Analysis of 2-grade Change in Palm/Sole Assessment from Baseline	Non-unique
14.2.5.1	ITT	Secondary Analysis: MMRM Analysis of Change from Baseline in Dermatology Life Quality Index	Non-unique
14.2.5.2	ITT	Secondary Analysis: MMRM Analysis of Change from Baseline in Children's Dermatology Life Quality Index	Non-unique
14.2.6.1.1	ITT	Secondary Analysis: Presence of Fissures on Palms or Soles	Unique
14.2.6.1.2	OLE ITT	Presence of Fissures on Palms or Soles	Unique
14.2.6.2.1	ITT	Secondary Analysis: Summary of Number of Fissures and Fissure Pain Level	Unique
14.2.6.2.2	OLE	Summary of Number of Fissures and Fissure Pain Level	Non-unique

Number	Population	Title	Unique/Non-unique
14.2.7.1	ITT	Exploratory Analysis: Summary of Change from Baseline in Ectropion Score	Unique
14.2.7.2	OLEITT	Summary of Change from Baseline in Ectropion Score	Non-unique
14.2.8.1	ITT	Exploratory Analysis: Change from Baseline in EQ-5D-5L	Non-unique
14.2.8.2	ITT	Exploratory Analysis: Change from Baseline in EQ-5D-Y	Non-unique

